Aim 2: Evaluate the impact of intervention condition on eating disorder symptoms. Hyp 2a. Participants in peer mentorship will have greater reductions in eating disorder symptoms, measured using the Eating Disorder Symptom Inventory (EPSI), compared to both control conditions. Hyp2b: For individuals who meet criteria for current or past anorexia nervosa, individuals assigned to peer mentorship will be more likely to achieve or maintain a BMI ≥ 18.5 , compared to both control conditions. Hyp2c: For individuals who meet criteria for current or past bulimia nervosa or binge eating disorder, individuals assigned to peer mentorship will be more likely to abstain from bingeing/purging and bingeing episodes, respectively, compared to individuals in either control condition.

Aim 3: Evaluate the impact of intervention condition on total cost for eating disorder treatment. Hyp 3. Estimated total cost for eating disorder treatment, measured using the Healthcare Utilization Survey, will be lower among peer mentorship participants compared to both control groups at (i) post-treatment and (ii) one-year follow up.

Exploratory Aim: Evaluate characteristics of individuals participating as peer and social support mentors. Exploratory hypothesis: Mentor characteristics and similarity between mentee and mentor characteristics will not influence mentee outcomes (acceptability, eating disorder symptoms, and estimated treatment cost).

Inclusion/Exclusion Criteria

This section details your study sample(s) and addresses the requirement for risk minimization. You may choose to divide your sample by population (healthy controls vs. subjects) or by procedure (subjects who will have an MRI) and then define different sets of criteria for each.

For each sample, create or insert a table to describe detailed criteria for study inclusion and exclusion and the method you will use to ascertain each criterion. The method of ascertainment may describe tests, scales and instruments. When relevant, indicate the level of training of the person who will make the assessment (e.g. clinical interview by a psychiatrist).

Inclusion/Exclusion Criteria needs to be numbered and listed in outline form (see Table template below)

Mentees (Adolescents or adults with anorexia nervosa, bulimia nervosa, or binge eating disorder):

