Eating Disorder Symptoms: Eating disorder symptoms will be assessed monthly using the Eating Pathology Symptoms Inventory (1). The Eating Pathology Symptoms Inventory (EPSI) is a self-report questionnaire that includes 45 items covering 8 subscales: Body Dissatisfaction, Binge Eating, Cognitive Restraint, Purging, Restricting, Excessive Exercise, Negative Attitudes toward Obesity, and Muscle Building. Each item is scored on a five-point Likert-style scale (0 = Never; 4= Often) to describe how well each item describes the participant's experiences. Scores are derived by summing responses across the questions included in each subscale. The EPSI is part of the Phynx Toolkit, a NHGRI/NIDA-sponsored catalog of recommended standard measures of phenotypes (symptoms) for use in biomedical research. To assess frequency of bingeing and purging episodes, BN and BED patients will be asked to report the average number of episodes/week experienced within the past month on each monthly report of symptoms.

Eating Disorders Quality of Life: Quality of life as related to the patient's eating disorder will be measured using the Eating Disorder Quality of Life assessment survey (2). The EDQOL is a 30-item measure assessing the impact of the eating disorder on psychological, physical/cognitive, financial and work/school domains of life. Participants indicate the extent to which the eating disorder has resulted in a variety of consequences within the past 30 days (e.g., "How often has your eating disorder led to low grades?" on a 5-point scale ranging from 1 = "never" to 5 = "always." Higher scores indicate higher levels of QOL impairment. The measure has been validated and demonstrates good psychometric properties.

Comorbid psychiatric symptoms: Anxiety symptoms will be measured using the State Trait Anxiety Inventory (STAI) (3).The STAI is a well-validated 20-item measure used to assess trait-level anxiety. Each item is rated on a scale of 0 – 2, with total scores ranging from 0 – 40. Depressive symptoms will be measured using the Patient Health Questionnaire-9 (PHQ-9), a 9-item self-report questionnaire commonly used in clinical practice. The PHQ has demonstrated good psychometric properties and has high sensitivity and specificity (4).

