Cover page

Official Title: Evaluation of the Communities of HEALing mentorship/support group program:
Assessment of preliminary efficacy

NCT number: NCT03317379

Document date: 3/23/2018

Statistical Analysis Plan

Intent-to-treat analyses will be used. Linear mixed models will be used to examine the relationship between group (peer, social support, wait list) and each outcome. Predictors in each model will be time, group, and their interaction. For all models, a random intercept will be included. The need for random slopes will be evaluated by examining model fit indices and testing the significance of the difference of the covariance estimate from zero. The peer group will be coded as the reference group to provide estimates and significance values for the difference between peer mentorship and each control condition.

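### Hyp 2c tests abstinence, but the only episode measure described is a self-reported weekly average with no stated response format, so one or two episodes a month may be recorded as zero.

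*Protocol*

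**What the plan says.** Under Specific Aims and Hypotheses, Aim 2, the protocol states Hyp 2c, which concerns the bulimia nervosa and binge eating disorder subgroups (present or past diagnosis): "individuals assigned to peer mentorship will be more likely to abstain from bingeing/purging and bingeing episodes, respectively". It appears among the primary aims and hypotheses. No threshold, recall window or time point for abstinence is given.

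Under Assessment Instruments, Eating Disorder Symptoms, one episode measure is described. Its purpose is given as "To assess frequency of bingeing and purging episodes", and its content as "BN and BED patients will be asked to report the average number of episodes/week experienced within the past month", collected monthly. Whether the answer is a whole number, a decimal or a category is not stated, nor whether bingeing and purging have separate fields. Both protocol summary forms in the file carry the same text.

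The EPSI is also completed monthly and has Binge Eating and Purging subscales. On response options the protocol says "Each item is scored on a five-point Likert-style scale (0 = Never; 4= Often", and on scoring "Scores are derived by summing responses across the questions included in each subscale". The protocol assigns the EPSI to Hyp 2a and does not link it to abstinence.

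The SAP says "Linear mixed models will be used to examine the relationship between group (peer, social support, wait list) and each outcome". It derives no abstinence variable.

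**The concern.** Abstaining means having no episodes. The natural measurement is a count that can be checked against zero, or a direct question on whether any episode occurred. The item described asks for an average per week over a month. For someone with one or two episodes in that month the true answer is a fraction below or about one half, and the easy whole-number answer is 0.

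That low-frequency range matters in this population. Mentees left inpatient, residential or partial hospital care within the past six months, and may have met diagnostic criteria only on entry to their most recent treatment. Occasional lapses are plausible, and an abstinence outcome exists to detect them. If lapses are entered as 0, the trial would report too much abstinence, and the contrast between arms would rest on a misclassified outcome.

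**Working it through.** The documents give no abstinence rate, effect size, alpha, power or sample-size calculation for Hyp 2c, so there is no figure of the plan's to reproduce. The check has two parts: exact arithmetic on the unit, and an illustration on assumed rates.

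**1. What the unit does to small counts**

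Input from the protocol: average episodes per week, over the past month. Formula: weekly average = k / w, where k is the number of episodes in the month and w the number of weeks (4 for a four-week month, 30/7 = 4.29, 31/7 = 4.43).

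| Episodes in month | w = 4 | w = 4.29 | w = 4.43 | As a whole number |
|---|---|---|---|---|
| 0 | 0.00 | 0.00 | 0.00 | 0 |
| 1 | 0.25 | 0.23 | 0.23 | 0 |
| 2 | 0.50 | 0.47 | 0.45 | 0 in a 30- or 31-day month; depends on the rounding rule when w = 4 |
| 3 | 0.75 | 0.70 | 0.68 | 1 |

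If fractions are accepted and used, zero is distinct from one and two. If answers are whole numbers, one episode a month always becomes 0, and two usually do.

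**2. What that could do to the comparison (assumed rates, not from the documents)**

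Let p be true abstinence in an arm and s the share of non-abstainers recorded as 0. Observed abstinence = p + (1 - p)s. This is never below p, so the recorded rate can only go up.

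Take true abstinence of 50% (peer) and 30% (control).

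*Equal s in both arms:* difference = (0.50 + 0.50s) - (0.30 + 0.70s) = 0.20(1 - s).
- s = 0: 50% vs 30%, 20 points
- s = 0.2: 60% vs 44%, 16 points
- s = 0.4: 70% vs 58%, 12 points

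For scale, a two-proportion comparison at two-sided 0.05 and 80% power (also assumptions) needs 93, 152 and 250 per arm in these three cases. The trial plans 80 completers over three arms, about 27 per arm (80/3), and Hyp 2c uses only the bulimia nervosa and binge eating disorder subset.

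*Unequal s:*
- s = 0.4 in peer, 0.2 in control: 0.50 + 0.50 × 0.4 = 0.70 and 0.30 + 0.70 × 0.2 = 0.44, a difference of 26 points, wider than the true 20
- s = 0.2 in peer, 0.4 in control: 0.60 and 0.58, a difference of 2 points

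The direction of bias is therefore not fixed.

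**3. How large s might be**

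The documents do not say. It depends on the response format and on how many non-abstainers have only one or two episodes a month, and neither is given.

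**The case against.** The strongest objection is that the unit does not by itself lose anything. An average of exactly 0 over a month is zero episodes. A reader might infer that the item cannot separate zero from one or two a month, but the documents do not support that. The protocol paraphrases the question and does not show the online form, which may accept decimals or offer an option for less than once a week. This stands, and the point is limited to what may happen.

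Second, no section says that abstinence is derived from this item; its stated purpose is frequency. This also stands. The link is an inference from the absence of any other episode count.

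Third, the monthly EPSI could serve as a cross-check: a non-zero Purging score beside a reported 0 per week would flag some errors. That is a partial help only. Subscale sums are not episode counts, and no such check is planned.

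Fourth, a reader might infer that misclassification must shrink the difference between arms. It need not. If peer mentorship lowers frequency among people who still binge or purge, more of them fall into the one-or-two range in that arm, and the difference could widen.

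**Conclusion.** The point holds as a measurement weakness of minor severity that is cheap to correct. Hyp 2c needs to know whether any episode occurred. The only episode measure described asks for a weekly average, has no stated response format, and is not accompanied by a definition of abstinence. One or two episodes a month equal 0.23-0.50 per week and may be recorded as 0.

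If that happens and a 0 is counted as abstinent, abstinence rates are inflated. The difference between arms shrinks if misclassification is equal across arms, as in the illustrative fall from 20 to 16 points at 20%, and may be biased either way if it is not. These figures rest on assumed abstinence rates and an assumed misclassification share. The documents allow no estimate of the true size, and they do not show that any misclassification will occur.

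**What to change.** In the monthly report, ask for the total number of binge episodes and, separately, the total number of purge episodes, either since the last report or in the past month. Alternatively, keep the present item and add a yes/no question on any binge and any purge episode. A fixed four-week window asked monthly is less suitable, because it leaves 2-3 days of each 30- or 31-day month uncovered (30 - 28 and 31 - 28).

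Define abstinence in the protocol and SAP as a count of zero over that window: binge and purge episodes for bulimia nervosa, binge episodes for binge eating disorder. State the time point at which it is assessed. If the weekly average is still wanted, derive it as the count divided by the number of weeks in the window; with a count, no information is lost.

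The cost is a small change to the online questionnaire and a short definition in the SAP. The downside is that responses already collected with the present item are not fully comparable. They should be flagged and handled in a sensitivity analysis, for example by repeating the comparison without them.

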Eating disorders are serious mental illnesses associated with significant morbidity and high relapse rates. Patients are at especially high risk of relapse after leaving structured treatment (e.g., hospitalization). Adjunct interventions targeting patients' motivation and participation in treatment at these times may help more patients recover from eating disorders. Project HEAL is a non-profit organization whose mission is to reduce suffering caused by eating disorders. Project HEAL has developed a intervention in which patient mentees with eating disorders are matched with peer mentors who have previously recovered from an eating disorder, and mentors meet weekly with mentees to provide support, guidance, and serve as a model that recovery is possible. Project HEAL has asked the researchers at the EDRU to help them evaluate the feasibility and effects of this intervention. Therefore, the purpose of the current study is to test whether peer-mentorship can help improve patients' eating disorder symptoms above and beyond their traditional treatment. The design of the study is a three-arm randomized controlled trial comparing peer mentorship to active (social-support) and wait-list control conditions. Participants in the study will be randomized to one of the three conditions for six months. Wait-list participants will subsequently receive either type of mentorship. Participants will complete assessments of their eating disorder symptoms at baseline, monthly throughout the course of the study, and one year after beginning the study. Outcomes will be compared between groups.

Please also paste of a copy of the Lay Summary into the PRISM PSF Form.

Background, Significance, and Rationale

In this section, provide a brief summary of the status quo of the relevant work field, and how the proposed study will advance knowledge. Specifically, identify the gaps in knowledge that your project is intended to fill. If no gaps exist that are obviously and directly related to your project, explain how your proposed research will contribute to the overall understanding of your field. Describe potential impacts of your project within your field of study and in a broader context. Provide a critical evaluation of existing knowledge. The literature review does not have to be exhaustive.

Anorexia nervosa and bulimia nervosa are serious mental illnesses associated with significant morbidity and high relapse rates. AN has the highest mortality rate of any psychiatric illness. Although family-based treatment has led to improved outcomes for adolescent patients, this therapeutic approach has only limited utility in adults. Research suggests that patients with EDs are at greatest risk for relapse in the first six month following discharge from an intensive treatment (e.g. hospitalization or residential). Adjunct, supportive approaches delivered at these high risk times have potential to improve eating disorder relapse prevention. Adjunct interventions also have potential to promote treatment engagement (attendance, compliance with meal plan, etc.) in patients with high ambivalence.

Project Heal® is a non-profit organization whose primary missions are providing grant funding for individuals with eating disorders who otherwise cannot afford treatment and promoting eating disorder recovery through campaigns and community programming. Project Heal has community sites (aka “chapters”) in 40 cities across the US and Canada. Project Heal recently launched a mentorship-based intervention at 12 of its sites, in which eligible individuals with eating disorders who are receiving treatment from a licensed professional are partnered for six months with peer mentors (individuals who have previously recovered from an eating disorder and who have participated in a general orientation/training program regarding the role of mentor). “Sites” refer to locations across the US and internationally where one or more individuals has established a local Project HEAL chapter. Chapters/“sites” range in size from just a few people to over 50. The Project HEAL national organization has ongoing contact with its sites about many different topics, including the Communities of HEALing program. In the past year, 12 sites have established Communities of HEALing programs, meaning that trained mentors carry out peer mentorship and free community support groups with oversight from a National-level Program Director. As more and more sites established peer mentorship programs, Project HEAL asked us to help them evaluate this intervention.

Moving forward, Project HEAL will continue to communicate with sites/chapters about any number of topics in addition to the Communities of HEALing study. From this point forward, all peer mentorship will take place in the context of the research study (mentorship will not be offered outside of the study). We will communicate with Project HEAL leadership to implement the study. All communication for the purpose of research assessments and data collection will be direct communication between EDRU research staff and study participants. We will provide supervision directly to peer mentors and social support mentors. We communicate directly with participants (and inform Project HEAL) regarding randomization (treatment assignment) and matching.

Project HEAL sites for its mentorship program currently include New York, Philadelphia, Los Angeles, San Francisco, Boston, Chicago, Essex, MA, Southeast Pennsylvania, and Pittsburgh. Interested participants who do not live in the vicinity of an existing Project HEAL site are offered available online peer mentors with whom they may communicate via FaceTime or Skype. Peer mentors provide support, guidance, and share personal experiences in order to help mentees cope with challenges to recovery and navigate day-to-day difficulties related to their eating disorder. Peer mentors and their mentees connect once per week in-person (for those from the areas described above) or online (for those who live outside of commutable distance from the identified sites) for one hour. Peer mentor/mentee interactions are focused on the mentee’s eating disorder recovery process, and includes structured topics/activities like examining pros and cons of behavior change and challenging eating disorder thoughts. Peer mentorship is *not* designed as a standalone intervention and requires participants in the program to be involved in concurrent treatment with a licensed professional.

Project HEAL’s mentorship program is one of the first programs of its kind. Given the project’s nascence, its acceptability and effectiveness have not been evaluated, and Project HEAL has asked Drs. [name] and [name] and the Columbia Eating Disorders Research Unit (EDRU) to evaluate it by conducting a randomized controlled trial comparing mentorship to two other conditions also carried out by Project HEAL. The two comparison programs are a non-eating disorder-focused social support condition (for six months) and a wait-list control (for six months). In the social support condition, individuals with an eating disorder are matched with a “social support mentor” without a history of an eating disorder. Social support mentors coordinate social activities within Project HEAL and the community, such as participating in advocacy or leisure activities. Participants assigned to this condition engage in an activity per week (lasting approximately one hour) with their social support mentor and in some cases, 1-2 other mentees. Interactions are centered on the week’s activity (e.g., writing a letter to a representative, viewing museum exhibit), with an *intentional focus outside the eating disorder*. Wait-list participants engage in treatment with their outpatient providers for six months (as do patients in both active conditions), and then they are offered a mentor for six additional months. They may choose whether they prefer a peer mentor or a social support mentor. Interventions were developed by Project HEAL and tailored to suit a research context with input from EDRU investigators. Program descriptions and manuals are provided for context.

To evaluate feasibility, we will monitor mentee attendance and acceptability in both active conditions. To evaluate fidelity, mentors and mentees will be asked to complete a brief form (Appendix 1, "weekly report") assessing meeting logistics (e.g., where the meeting occurred, number of contacts per week outside of meeting) and content of the meeting (e.g., topics discussed, activities). Peer mentors will be asked to complete an additional questionnaire assessing adherence to the peer-mentorship manual (Appendix 2, post-meeting mentor rating). Participants' eating disorder symptoms, comorbid psychiatric symptoms, and health care costs and utilization will be assessed at pre- mid- and post-treatment to evaluate preliminary efficacy. Participants' weight and BMI trajectories will also be evaluated by obtaining weight measures from the participant's outpatient provider with participant permission. Outcomes for individuals who participate in the peer mentorship program will be compared with individuals who participate in the social support and wait-list conditions.

Specific Aims and Hypotheses

Concisely state the objectives of the study and the hypothesis or primary research question(s) being examined. There should be one hypothesis for every major study procedure or intervention. For pilot studies, it is important not to overstate the study's objectives. If there are no study hypotheses, describe broad study goals/aims.

Primary Aims and Hypotheses:

Aim 1. Evaluate the feasibility and acceptability of peer mentorship. Hyp 1a. Peer mentorship will demonstrate greater feasibility, as measured by higher attendance rates, compared to the active control intervention. Hyp 1b. Peer mentorship will demonstrate greater acceptability, as measured by higher acceptability ratings, compared to both control conditions.

Aim 2: Evaluate the impact of intervention condition on eating disorder symptoms. Hyp 2a. Participants in peer mentorship will have greater reductions in eating disorder symptoms, measured using the Eating Disorder Symptom Inventory (EPSI), compared to both control conditions. Hyp2b: For individuals who meet criteria for current or past anorexia nervosa, individuals assigned to peer mentorship will be more likely to achieve or maintain a BMI ≥ 18.5 , compared to both control conditions. Hyp2c: For individuals who meet criteria for current or past bulimia nervosa or binge eating disorder, individuals assigned to peer mentorship will be more likely to abstain from bingeing/purging and bingeing episodes, respectively, compared to individuals in either control condition.

Aim 3: Evaluate the impact of intervention condition on total cost for eating disorder treatment. Hyp 3. Estimated total cost for eating disorder treatment, measured using the Healthcare Utilization Survey, will be lower among peer mentorship participants compared to both control groups at (i) post-treatment and (ii) one-year follow up.

Inclusion/Exclusion Criteria

This section details your study sample(s) and addresses the requirement for risk minimization.

You may choose to divide your sample by population (healthy controls vs. subjects) or by procedure (subjects who will have an MRI) and then define different sets of criteria for each.

For each sample, create or insert a table to describe detailed criteria for study inclusion and exclusion and the method you will use to ascertain each criterion. The method of ascertainment may describe tests, scales and instruments. When relevant, indicate the level of training of the person who will make the assessment (e.g. clinical interview by a psychiatrist).

Inclusion/Exclusion Criteria needs to be numbered and listed in outline form (see Table template below)

Mentees (Adolescents or adults with anorexia nervosa, bulimia nervosa, or binge eating disorder):

**Note that all EDRU screens will be reviewed with a clinician (MD or PhD level) and if any criteria are in question, the clinician will speak directly with the potential participant by telephone.*

CRITERION	METHOD OF ASCERTAINMENT
Inclusion:	
1. Ages 14 – 45 years	Initial telephone interview with Project HEAL staff, confirmation during telephone screening with EDRU research team member (RA level or higher)*
2. Meets criteria for current or past anorexia nervosa, bulimia nervosa , or binge eating disorder (criteria met either presently or at time of entry into treatment for most recent treatment course)	Eating Disorder Assessment -5 (administered by EDRU RA* during telephone screening)
3. Recent (within past 6 m) discharge from inpatient, residential, or partial hospitalization program (PHP)	Initial telephone interview with Project Heal staff, confirmation during telephone screening with EDRU RA*
4. Involved in outpatient treatment at an appropriate level of care	Telephone screening with EDRU RA* and Documentation from primary outpatient clinical provider using Provider Form
5. Medical stability	Telephone screening with EDRU RA* and Documentation from primary outpatient clinical provider using Provider Form
6. Access to Smart Phone or computer to complete study assessments	Telephone screening
Exclusion:	
1. Evidence of needing specialized treatment for another medical or mental health condition or substance use	Telephone screening with EDRU RA*

Mentors:

Mentors in the peer-mentorship group are adults who have recovered from an eating disorder, while mentors in the social support group are adults who never had an eating disorder. All mentors are individuals recruited and trained by Project Heal to do volunteer work within their organization.

Inclusion/Exclusion criteria: n/a.

Study Procedures

Provide a clear, concise narrative of study procedures with special attention to the subjects' involvement. Detail the overall study timeline and location of study procedures, list all interventions, assessments and interviews, estimate the duration of each procedure, provide dosing schedules, identify study personnel involved in each procedure, and provide

credentials for relevant personnel. For complicated study designs, we strongly encourage attaching tables, flow-charts, and study algorithms.

[figure not shown]
The design of the study is a three-arm, randomized controlled trial comparing peer mentorship to an active control condition that is not focused on eating disorder symptoms (social support), and a wait-list control. Feasibility, as well as preliminary efficacy for improving eating disorder symptoms and reducing health care costs, will be evaluated.

Recruitment

Participants will be recruited into a study examining the effectiveness of two Communities of Healing adjunct programs, peer mentorship and social support, for promoting eating disorder recovery alongside traditional outpatient eating disorder treatment. Participants with eating disorders (mentees) will be recruited using strategies found to be effective in launching the first Communities of HEALing programs including referrals from providers and utilizing the organizations various online platforms (websites, Facebook). Through Project HEAL's involvement in providing grant funding to patients seeking eating disorders treatment, Project HEAL has established relationships with eating disorder professionals and centers. In the 1-2 weeks preceding patients' discharge from hospital/IOP treatment, providers will inform patients about the study and inquire whether the patient is interested. Interested participants will be given information about the study (according to the attached document "Recruitment messaging for Communities of HEALing") and provided EDRU contact information. EDRU research staff will manage study screening and enrollment. The study will also be advertised through Project HEAL's social media platforms (e.g., website, Facebook) using approved recruitment language (see document "Recruitment messaging for Communities of HEALing").

Procedure

Overview of study flow

EDRU Screening: A trained, EDRU research assistant with a bachelor's degree or higher will screen and consent all participants by telephone. RAs performing telephone consent will have a BA or higher and research ethics/CITI training. Prior to conducting telephone consent, independently, RAs will first observe an investigator or senior-level RA conduct telephone and will be observed by an investigator or senior-RA to ensure competence. They will first obtain participant's verbal consent to conduct the telephone screening. During the telephone screening, the EDRU research staff member (RA level or higher) will assess inclusion/exclusion criteria including presence of an eating disorder using a standardized measure (the EDA-5). RAs will review eligibility with an EDRU clinician (MD or PhD).

Potential participants who are interested will be provided a copy of the consent form by mail or email, according to their stated preference. If mailed, the telephone consent will not be conducted until the participant indicates that they have received the hard copy. After the participant has received copies, the RA will review the consent (and assent, if applicable) forms, including nature and purpose of study, procedures, potential risks/benefits, and confidentiality, with the participant (and parent/guardian, if applicable). All consenters are NYSPI staff. Potential participants will be given an opportunity to ask questions and questions will be answered by the EDRU research staff member (RA level of higher). Participants will indicate whether they wish to participate and consent will be documented by the EDRU RA. For participants who are 14 – 17 years old, parental consent and adolescent assent will be documented. We have requested a waiver for documentation of consent.

Additional pre-intervention procedures: Prior to study enrollment, participants will complete several questionnaires and provide documentation from their treatment team. Questionnaires will be administered using Qualtrics, a HIPAA-compliant application accessible by computer or smart phone, by which participants can access and complete online surveys. Assessment measures are described in detail below in the Assessment Instruments section. They will be used to assess baseline eating disorder symptoms, co-morbid psychiatric symptoms and health care cost and utilization. Participants will provide contact information for their primary provider and document his/her consent to contact his/her primary provider. Similar to consent forms, consent to speak with primary providers will be obtained verbally and signed hard copies will be collected. Primary outpatient treatment providers will be asked to complete a baseline medical evaluation form documenting that, in his/her opinion, the patient is enrolled in treatment *at a sufficient level of care given*. The form on which this information will be document is attached as an addendum (Appendix 3). Treatment providers will also be asked to provide documentation of the patient's medical stability. On a monthly basis, providers will be contacted by EDRU staff and asked to report the participant's height and weight and confirm medical stability and continued treatment engagement.

Interventions:

After a participant has signed consent and completed baseline screening measures, he or she will be randomized to a condition. Randomization schema will be developed and executed by EDRU research team. The participant will then be matched with an available mentor. Matching is based on geographic location and when possible, age, gender, and diagnostic subtype, (e.g., an individual with anorexia nervosa would not be matched with a mentor who has binge eating disorder). Participants will enter the study on a rolling basis. After a participant is assigned to a condition, he or she will be contacted by Project HEAL staff and informed of treatment assignment. Participants assigned to mentorship or social support will be instructed that he/she will be contacted by his/her mentor/PH volunteer within five days.

Active intervention conditions

Participants in both peer mentorship and social support will have weekly contact with a peer or social support mentor. Mentor/mentee pairs will meet in public or semi-public locations, including those on college campuses. Examples of possible meeting locations include libraries, coffee shops, parks, common spaces in residential settings (such as an apartment lobby or meeting room). Many mentor/mentee pairs are anticipated to be members of university communities and may utilize public spaces such as dormitory common areas, meeting rooms, university libraries, or study lounges. If a pair arrives to an arranged meeting location and it is crowded and/or does not appear private, mentors will be trained to say "We may want to meet in a more private space," and mentees will be queried whether they wish to move to an alternative location. Whenever possible, pairs will meet in private spaces.

Peer Mentorship

The mentorship intervention includes mentorship of patients with an eating disorder by those who have recovered from an eating disorder. All mentors have a history of an eating disorder but no longer meet criteria for an eating disorder. The peer mentorship program being studied was developed by Project HEAL. It is based on a program designed by [name], MA, Med, FAED (Appendix 4). [name] founded Monte Nido, the first licensed residential eating disorder treatment center. For many years she has provided training in this model to recovered individuals who went on

to serve as mentors. Per the Project Heal Mentor Training Handbook (Appendix 4 and 5), mentors will act as a support person and role model for the mentee, through providing interpersonal support, guidance, and sharing of wisdom from personal experiences. Interactions between mentors and mentees are guided by eight core principles used to promote eating disorder recovery, each of which has suggested objectives (e.g., help those still struggling to examine the cost/benefits of recovering) and activities (e.g., write ten goals for treatment, write about a day in my life when I am recovered). The mentors will keep track of which principles, topics, and activities addressed in each mentee meeting using a post-meeting mentor rating form filled out by the mentor after each meeting (Appendix 2). Mentees and mentors connect once per week in person. If both parties agree to exchange contact information, then mentor/mentee pairs may also connect via phone or text. All phone utilization charges are billed to the participant's own phone plan and will not be covered by Project HEAL. Adaptations to Project HEAL's peer mentorship program are solely for the purposes of research.

Social support

Social support mentors (Project HEAL volunteers) will not have a history of an eating disorder. Social support mentors coordinate social activities within Project HEAL and the community, such as participating in advocacy (e.g., writing a letter to a congressperson) or attending a leisure activity (e.g., a museum), as per the social support manual (Appendix 6). Mentees engage in one activity per week (lasting about one hour), with the Project HEAL volunteer, and in some cases, one to three other mentees. Interactions are centered around the week's activity.

Wait-list control

To promote retention, participants will be contacted at two and five months by Project HEAL staff members, who will remind the participant of the study timeline, indicate when the next assessment will be completed, and remind the participant that he/she will be assigned to an active intervention after the 6-month study period.

Addressing mentee/mentor mismatch: There is a 3-step procedure for addressing instances in which a mentee reports a mismatch with his/her mentor. First, the mentor would receive supervision and make attempts to resolve the mismatch. Second, if the mismatch persists, we will match the mentee with a new mentor one time only. If a mentee has a mismatch with their second mentor, they will not be eligible to be re matched and their participation in the study interventions (mentorship) will be discontinued. If the mismatch occurs because the mentee is not abiding by guidelines for participation and this causes the mentor to feel uncomfortable, the PI/Co-I will speak with the mentee to address the issue. If this persists, the mentee's participation in the mentorship component of the study will be discontinued. Mentee guidelines are attached.

Operationalized criteria for early discontinuation of the active intervention: Grounds for discontinuing the active interventions (meaning that the participant is no longer able to meet with his/her mentor) include the following:

- (a) Not complying or attending outpatient treatment (defined as mentee or provider indicating that the mentee is not attending treatment for 2 weeks or more) or not hearing from the mentee's treatment provider for 2 consecutive months.
- (b) Requiring a higher level of care (per the mentee's treatment provider) and choosing not to pursue it.
- (c) Missing 3 consecutive sessions with mentor and/or missing >2sessions/month for 2 consecutive months (without calling ahead to reschedule).
- (d) Requesting >1 mentor reassignment. If the mentee has a mismatch with >1 mentor, we will not be able to assign a third mentor.

If a mentee is recommended for, and enters, treatment at a higher level of care, he/she may not receive mentorship while receiving treatment at the higher level of care. After discharge, pt may attend any remaining mentorship sessions falling within the study period (months 1 – 6) after providing a new provider clearance form. If the mentee was assigned to the wait list and enters treatment at a higher level of care during months 6 – 12, the same procedure will be followed. We will ask study participants to continue completing questionnaires even if a participant is no longer meeting with

his/her mentor (regardless of the reason). Patients may choose whether they wish to continue completing study assessments.

Common intervention components

